- Serial blood PK sampling will be performed for the first dose of study treatment on Day 1 and for the time-matched dose on Day 4. Blood samples will be collected predose and at 0.5, 1, 1.5, 2, 3, 4, 6, 8, and 12 hours postdose.
- Serial urine PK sampling will be performed for the first dose of study treatment on Day 1 and for the time-matched dose on Day 4. Urine samples will be collected predose and at intervals of 0 to 2 hours, 2 to 4 hours, 4 to 6 hours, 6 to 8 hours, 8 to 10 hours, and 10 to 12 hours postdose.
- Predose PK blood samples will be collected before each time-matched dose on Days 1 through 5. Predose PK urine samples will be collected 0 to 2 hours before each time-matched dose on Days 1 through 5. Only 1 sample is needed when serial and predose samples overlap.
- Participants will check-out of the clinic after all study procedures have been performed, including a predose clean-catch midstream urine sample for Gram stain, quantitative bacteriology culture, and antimicrobial susceptibility testing, predose PK sample collections, and safety assessments. Participants should remain in the clinic to complete a total of 10 doses. Participants will be instructed to return for the TOC (Day 10 to 13) and Follow-up (Day 28±3) Visits.

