2.3. Study Design

Overview of Study Design and Key Features

The study design schematic is shown in [Figure 1](#).

Figure 1 Study Design Schematic

BID=twice daily; PK=pharmacokinetic; TOC=test of cure; WBC=white blood cell.

- Serial blood PK sampling will be performed for the first dose of study treatment on Day 1 and for the time-matched dose on Day 4. Blood samples will be collected predose and at 0.5, 1, 1.5, 2, 3, 4, 6, 8, and 12 hours postdose.
- Serial urine PK sampling will be performed for the first dose of study treatment on Day 1 and for the time-matched dose on Day 4. Urine samples will be collected predose and at intervals of 0 to 2 hours, 2 to 4 hours, 4 to 6 hours, 6 to 8 hours, 8 to 10 hours, and 10 to 12 hours postdose.
- Predose PK blood samples will be collected before each time-matched dose on Days 1 through 5. Predose PK urine samples will be collected 0 to 2 hours before each time-matched dose on Days 1 through 5. Only 1 sample is needed when serial and predose samples overlap.

Participants will check-out of the clinic after all study procedures have been performed, including a predose clean-catch midstream urine sample for Gram stain, quantitative bacteriology culture, and antimicrobial susceptibility testing, predose PK sample collections, and safety assessments. Participants should remain in the clinic to complete a total of 10 doses. Participants will be instructed to return for the TOC (Day 10 to 13) and Follow-up (Day 28±3) Visits

Design Features	
 • A Phase IIa single-center, open-label, repeat dose PK study. • The study duration is approximately 28 days comprising approximately 5 days of confinement at the clinic followed by 2 outpatient visits 
 ○ Clinic Confinement Visits 
 ▪ Baseline (Day -1 to Day 1 predose) Visit ▪ On-Therapy (Day 1 to Day 5) Visit ○ Outpatient Visits 
 ▪ TOC (Day 10 to 13) Visit ▪ Follow-up (Day 28) Visit • Approximately 25 to 30 participants will be enrolled to achieve approximately 20 participants who complete the study assessments through Day 5 and are evaluable for the PK analyses.
------------------------	--

Dosing	
 All participants who meet the study entry criteria and provide informed consent will receive oral gepotidacin 1500 mg (2 × 750-mg tablets) BID for 5 days (total of 10 doses).

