7.2.1.2. Derived Urine Pharmacokinetic Parameters

Pharmacokinetic parameters will be calculated by standard non-compartmental analysis according to current working practices and using the currently supported version of SAS version 9.3. All calculations of non-compartmental parameters will be based on actual sampling times. Pharmacokinetic parameters listed will be determined from the urine concentration-time data, as data permits.

Table 3 Derived Urine Pharmacokinetic Parameters

Parameter	Parameter Description
Ae 12h	Total unchanged drug excreted over 12 hours (total amount of drug excreted in urine), calculated by adding all the fractions of drug collected over all the allotted time intervals. Calculated from Days 1 and 4.
Ae(t1-t2)	Amount of drug excreted in urine in time intervals for predose, 0 to 2 hours, 2 to 4 hours, 4 to 6 hours, 6 to 8 hours, 8 to 10, and 10 to 12 hours postdose. Calculated from Days 1 and 4.
AUC(0-τ)	Area under the urine concentration-time curve (AUC) from time 0 to the 12-hour dosing interval, to be calculated using the linear trapezoidal rule for each incremental trapezoid and the log trapezoidal rule for each decremental trapezoid. Calculated from Days 1 and 4.
AUC(0-24)	Area under the urine concentration-time curve (AUC) from time 0 to the 24-hour, calculated as: $AUC(0-24) = AUC(0-\tau) \times 2$ Calculated Day 4.
fe%	Percentage of the given dose of drug excreted in urine, calculated as: $fe\% = (Ae\ 12h/Dose) \times 100$ Calculated for Days 1 and 4
CLr	Renal clearance of drug, calculated as: $CLr = Ae\ 12h/AUC(0-\tau)$ Calculated from Days 1 and 4.
C _τ	Observed predose (nominal time = 0) urine concentrations on Days 1 through 5.

NOTES:

- Additional parameters may be included as required.

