10. PHARMACOKINETIC / PHARMACODYNAMIC ANALYSES

Relationships between the ratio of Day 4 free plasma and urine PK parameters to baseline MIC (free plasma AUC(0-24)/MIC, free plasma C_{max}/MIC, urine AUC(0-24)/MIC and urine C_{tau}/MIC) and PD measures (therapeutic response) will be explored in tabular and graphical format.

Summary statistics (arithmetic mean, geometric mean, median, SD, minimum, maximum, and CV) for free plasma and urine PK parameters to baseline MIC values will be summarized by uropathogen and therapeutic response, as appropriate. Free plasma and urine PK parameters to baseline MIC values will be listed by uropathogen and therapeutic response for individual participants.

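### SAP Table 3 integrates pooled 2-hour urine collections as if they were point samples: Day 1 urine AUC comes out low, and Day 4 urine AUC depends on a time convention the SAP does not state

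*SAP*

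**What the plan says.** Both documents describe urine PK sampling on Days 1 and 4 as interval collections: "Urine samples will be collected predose and at intervals of 0 to 2 hours, 2 to 4 hours, 4 to 6 hours" and so on to 10 to 12 hours (Protocol 5.1; SAP 2.3 matches).

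SAP 7.2.1.2, Table 3, then treats these collections in two ways:

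- **As intervals.** The 12-hour amount excreted is "calculated by adding all the fractions of drug collected over all the allotted time intervals".
- **As points.** Urine AUC(0-τ) is defined as "Area under the urine concentration-time curve (AUC) from time 0 to the 12-hour dosing interval, to be calculated using the linear trapezoidal rule"; in full, the rule is "the linear trapezoidal rule for each incremental trapezoid and the log trapezoidal rule for each decremental trapezoid", the same rule that SAP Table 2 gives for plasma.

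On timing, the section says only "All calculations of non-compartmental parameters will be based on actual sampling times". The time-zero value is taken from "Observed predose (nominal time = 0) urine concentrations on Days 1 through 5".

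Urine AUC(0-τ) is derived on Days 1 and 4. Urine AUC(0-24) is twice AUC(0-τ) and is derived on Day 4 only. SAP Section 10 builds its ratios to baseline MIC from Day 4 parameters.

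**The concern.** A trapezoid joins concentrations observed at known instants. A pooled 2-hour urine concentration is an average over the urine formed in that interval, so its natural contribution to the area is concentration × duration. To apply a trapezoid, someone must first assign each value a time, and the SAP does not say which. The schedule does not settle it either: in Protocol Table 2 and SAP Table 10 the urine marks appear to sit in the columns for the interval starts, and no rule for the AUC follows from that. Two programmers working from the same text could report different urine AUCs from the same data.

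The rule also brings in the predose value, which the interval sum does not need. On Day 1 it is zero, because previous treatment with gepotidacin is excluded (Protocol 6.2, criterion 28). On Day 4 it is a trough. The log-down step assumes exponential decline between two instants, whereas a fall in urine concentration may also reflect dilution.

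What is at stake is the descriptive urine AUC on each day and, through Day 4, the urine AUC/MIC displays. Urine AUC/MIC is also the type of index on which Protocol 5.5 bases the dose rationale.

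**Working it through.** **The documents' own figure.** Protocol 5.5 gives a minimum urine fAUC over 24 h of 1610 µg·h/mL (2 × 807 = 1614, rounded), an MIC of 4 µg/mL and a target of 275. Then 1610/4 = 402.5 and 402.5/275 = 1.46, which agrees with the stated margin of approximately 1.5-fold.

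**Identities that need no PK assumptions.** Let C1 to C6 be the six interval concentrations and C0 the predose value.

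- Reference (concentration × duration): 2·ΣCi.
- Linear trapezoid, values at interval ends: 2·ΣCi + C0 − C6.
- Linear trapezoid, values at midpoints: 2·ΣCi + 0.5·(C0 − C1) − C6 + whatever is added for 11 to 12 h.
- Log-down lowers either result further wherever the concentration falls.

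On Day 1, C0 = 0, so the end-time result is low by C6 plus the log-down deficit.

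**Worked record (illustrative).** Interval values are 300, 500, 250, 130, 80 and 50 µg/mL. The reference is 2 × 1310 = 2620 µg·h/mL.

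- Day 1, end times: 300 + 800 + 721.3 + 367.0 + 206.0 + 127.7 = 2522, or −3.7%. The linear rule alone gives 2620 + 0 − 50 = 2570, so 50 of the shortfall is C6 and about 48 is log-down.
- Day 1, midpoints: the first trapezoid covers 1 h, 0.5 × (0 + 300) = 150. The total to 11 h is 2372 (−9.5%). Log-linear extrapolation to 12 h adds about 44.6, giving 2417 (−7.8%).
- Same six values, predose 50 (a Day 4 case with C0 = C6): end times 2572 (−1.8%); midpoints 2397 (−8.5%), or 2442 (−6.8%) if extrapolated.
- Same six values, predose 100: end times 2622 (+0.1%).

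**Range over assumed profiles.** The documents give no urine profile. Assumed here: first-order absorption 0.8 to 3 per hour, half-life 2 to 9 h, 12-hourly dosing, Day 4 as the seventh dose, constant urine flow. Bias of the SAP rule against 2·ΣCi:

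| Time convention | Day 1 | Day 4 |
|---|---|---|
| Interval end | −2.8% to −6.6% | −0.1% to −2.1% |
| Midpoint, extrapolated to 12 h | −3.6% to −13.3% | −1.7% to −12.9% |
| Midpoint, stopped at 11 h | −8.9% to −14.1% | −7.4% to −13.7% |

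With flow also varying between intervals (log-SD 0.5, 4000 simulated profiles), end times gave a mean of −6.3% on Day 1 (none positive) and −2.7% on Day 4 (14% positive). Midpoints extrapolated to 12 h gave −9.0% and −7.6% (1% positive on Day 4).

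**Sign on Day 4.** With end times and constant flow, the bias turned positive in the four profiles tested once the predose concentration exceeded the 10 to 12 h concentration by 1.06- to 1.39-fold. At 2-fold it was +1.4% to +4.4%.

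**The case against.** The strongest reply is that nothing decided in this trial turns on the point. Urine AUC is not among the listed primary or secondary endpoints, the AUC/MIC work is tabular and graphical, and no test or target-attainment rule uses it. An error of a few percent is small beside the two-fold steps in which MIC is measured. All of this stands, and it keeps the point a minor one.

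The benchmark can also be challenged. Concentration × duration equals the time integral only if flow is steady within each collection, and the simulation assumed that. This is fair, but the trapezoid works from the same pooled values and adds further assumptions about timing and decay.

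Four stronger readings are tempting and are not supported:

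- *The Day 1 bias, or the difference between days, distorts AUC/MIC.* The ratios use Day 4 only. No planned analysis contrasts the two days' urine AUC; they are only summarised by study day.
- *Urine AUC/MIC is always understated.* On Day 4 the size depends on the unstated convention, and with end times the sign is not fixed.
- *Half of the first interval is lost.* With end times the 0 to 2 h value is used again in the next trapezoid; the net linear loss on Day 1 is C6.
- *The 1.5-fold margin is wrong.* It comes from an earlier Phase I study whose AUC method is not shown, and this SAP cannot bias it. Purely for scale, −2% to −14% would move 1.46 to between 1.43 and 1.26, still above 1.

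**Conclusion.** The concern holds in a limited form. Table 3 applies a point-sample rule to interval collections and leaves the time assignment open. Day 1 urine AUC(0-τ) is biased low under both conventions in every profile tested: about 3% to 7% with end times and 4% to 14% with midpoints. Day 4 urine AUC(0-τ) is low by about 0% to 2% with end times and about 2% to 14% with midpoints, usually but not always low for an individual. That spread arises largely from a choice the SAP does not make.

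The identities are exact. The percentages rest on assumed profile shapes and, in the table, on constant flow. The effect is confined to descriptive urine AUC summaries and exploratory PK/PD. This takes the AUC(0-τ) in the renal clearance formula to be the plasma one; Table 3 itself defines only a urine AUC(0-τ), so that label deserves a separate clarification.

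**What to change.** In SAP Table 3, define urine AUC(0-τ) as the sum, over the six postdose collections, of concentration × actual collection duration (end minus start). Set it to missing if any collection is lost or incomplete. Keep AUC(0-24) as twice the Day 4 AUC(0-τ), and keep the linear/log trapezoid for plasma only. No assigned time, time-zero value or rule for 11 to 12 h is then needed, and the definition matches how the same table already sums amounts excreted.

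The cost is small: one line of text and simpler code. Protocol 9.5.1 already requires the actual date and time of each collection; the sponsor should confirm that both start and end are captured. There are two downsides. A lost collection now gives a missing value where a trapezoid would have bridged the gap. Comparison with earlier studies is also less direct if they used trapezoids; a footnoted trapezoid value with its time convention stated would deal with that.

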7.1.1.2. Derived Pharmacokinetic Parameters

Pharmacokinetic parameters will be calculated by standard non-compartmental analysis according to current working practices and using the currently supported version of Phoenix WinNonlin version 6.4 or higher. All calculations of non-compartmental parameters will be based on actual sampling times. Pharmacokinetic parameters listed will be determined from the plasma and urine concentration-time data, as data permits. [Table 2](#) provides the details of derived plasma PK parameters.

Table 2 Derived Plasma Pharmacokinetic Parameters

Parameter	Parameter Description
AUC(0- τ)	Area under the concentration-time curve (AUC) from time 0 to the 12-hour dosing interval, to be calculated using the linear trapezoidal rule for each incremental trapezoid and the log trapezoidal rule for each decremental trapezoid. Calculated from Days 1 and 4.
AUC(0-24)	Area under the concentration-time curve (AUC) from time 0 to the 24-hour, calculated as: $AUC(0-24) = AUC(0-\tau) \times 2$ Calculated for Day 4.
C _{max}	Maximum observed concentration, determined directly from the concentration-time data. Calculated from Days 1 and 4.
T _{max}	Time to first occurrence of C _{max} . Calculated from Days 1 and 4.
CL _{ss} /F	Apparent steady state clearance (Day 4 only), calculated as $CL_{ss}/F = \text{Dose}/AUC(0-\tau)$
R _o	Accumulation ratio (Day 4 only), calculated as: $R_o = AUC(0-\tau) \text{ Day 4}/AUC(0-\tau) \text{ Day 1}$
C _{τ}	Observed predose (nominal time = 0) concentrations on Days 1 through 5

NOTES:

- Additional parameters may be included as required.

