12.3.3. Reporting Standards for Pharmacokinetic

Pharmacokinetic Concentration Data	
PC Windows Non-Linear (WNL) File	PC WNL file (xpt format) for the non compartmental analysis will be created according to SOP 314000(2.0). Note: Concentration values will be imputed as per GUI_51487
Descriptive Summary Statistics, Graphical Displays and Listings	Refer to IDSL PK Display Standards. Refer to IDSL Statistical Principle 6.06.1. Note: Concentration values will be imputed as per GUI_51487 for descriptive summary statistics/analysis and summarized graphical displays only.
Pharmacokinetic Parameter Derivation	
PK Parameter to be Derived by Programmer	The following plasma PK parameters will be derived by the Programmer: R ₀ , C _τ The following urine PK parameters will be derived by the Programmer: Ae 12h, Ae(t1-t2), Fe%, CL _r , C _τ
Pharmacokinetic Parameter Data	
Is NQ impacted PK Parameters Rule Being Followed	Yes, refer to [Standards for Handling NQ Impacted PK Parameters].
Descriptive Summary Statistics, Graphical Displays and Listings	Refer to IDSL PK Display Standards.

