12.9.8. Pharmacokinetic Tables

Pharmacokinetic: Tables					
No.	Population	IDSL / Example Shell	Title	Programming Notes	Deliverable
Pharmacokinetic Concentrations					
4.1.	PK Concentration	PKCT1	Summary of Gepotidacin Plasma Pharmacokinetic Concentration-Time Data (units)		SAC
4.2.	PK Concentration	PKCT1	Summary of Gepotidacin Urine Pharmacokinetic Concentration-Time Data (units)		SAC
4.3.	PK Concentration	PKCT1	Summary of Gepotidacin Cervical, Rectal, and Pharyngeal Pharmacokinetic Concentration-Time Data (units)		SAC
Pharmacokinetic Parameters					
4.4.	PK Parameter	PKPT4	Summary Statistics of Derived Gepotidacin Plasma Pharmacokinetic Parameters	Free and total PK Parameters include: AUC(0-tau) (units), AUC(0-24) (units), Cmax (units), Tmax (units), CLss/F (units), Ro (units), Ctau (units). Do not In-transform Tmax. Ctau will have values for Day 1 through 5	SAC
4.5.	PK Parameter	PKPT4	Summary Statistics of Derived Gepotidacin Urine Pharmacokinetic Parameters	Parameters include: Ae12h (units), A(t1-t2) (units), %fe (units), CLr (units), Ctau (units), AUC(0-tau) (units), and AUC(0-24) (units) for all subjects; Ae(t1-t2) include Ae(0-2) (units), Ae(2-4) (units), Ae(4-6) (units), Ae(6-8) (units), Ae(8-10) and Ae(10-12) (units). Ctau has values on Day 1 through Day 5	SAC
4.6.	PK Parameter	PK_T1	Statistical Analysis of Gepotidacin Plasma Predose	Ctau values of day 1 through 5	SAC

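### SAP Table 3 divides Ae 12h by an AUC(0-τ) that the same table defines on urine, so CLr as written is a urine flow rate and not a renal clearance

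*SAP*

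**What the plan says.** SAP Section 7.2.1.2, Table 3, lists the urine parameters. Its AUC(0-τ) row reads "Area under the urine concentration-time curve (AUC) from time 0 to the 12-hour dosing interval", calculated for Days 1 and 4. The CLr row begins "Renal clearance of drug, calculated as" and gives Ae 12h/AUC(0-τ), also for Days 1 and 4, with no reference to plasma or to Table 2. The numerator, Ae 12h, is "calculated by adding all the fractions of drug collected over all the allotted time intervals". The text introducing the table says: "Pharmacokinetic parameters listed will be determined from the urine concentration-time data, as data permits".

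SAP Section 7.1.1.2, Table 2, uses the same symbol for the plasma quantity: "Area under the concentration-time curve (AUC) from time 0 to the 12-hour dosing interval". SAP Section 7.1.1.1 also derives unbound plasma concentrations as 0.67 times total, and the programming note for Table 4.4 (SAP Section 12.9.8) asks for both free and total plasma parameters.

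SAP Section 12.3.3 has a line starting "The following urine PK parameters will be derived by the Programmer", and CLr is on that list. Table 4.5 in SAP Section 12.9.8 reports CLr alongside urine AUC(0-τ) and AUC(0-24). The protocol (Sections 4, 9.5.1 and 10.3.1) names CLr as a secondary parameter on Days 1 and 4 but gives no formula.

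**The concern.** One symbol stands for two different, separately reported quantities, and the CLr row sits in the table where that symbol means the urine area. The word urine is not a slip for plasma: urine AUC(0-24) is twice urine AUC(0-τ), and SAP Section 10 uses it in the exposure/MIC ratios. A programmer who takes Table 3 as the specification would therefore divide the amount in urine by the area under the urine concentration curve.

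That quotient has units of volume per time, as a clearance does, so a unit check would pass. It depends on how much urine the participant makes, and hence on fluid intake, and not on renal elimination of gepotidacin. At stake is a secondary endpoint that would be mislabelled for every participant on both days.

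**Working it through.** The documents state no value of CLr, so there is no planned figure to reproduce. The check is of the formula, followed by its size.

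**1. Algebra.** Let Cu be urine concentration, Q urine flow and Cp plasma concentration.

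- Mass balance in urine: Ae = ∫ Cu·Q dt. Hence Ae / ∫ Cu dt is the mean urine flow weighted by Cu, and equals Q when flow is constant.
- Definition of renal clearance: excretion rate = CLr·Cp, so Ae = CLr·∫ Cp dt and CLr = Ae / plasma AUC over the same interval.

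**2. Simulation.** A one-compartment oral model was run over 12 h with a 1500-mg dose. The other inputs are assumptions chosen for illustration: absorption rate 1.0 per h, volume 200 L, non-renal clearance 30 L/h, bioavailability 0.45. True CLr and urine flow were varied.

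| True CLr (L/h) | Urine flow (L/h) | Ae / plasma AUC (L/h) | Ae / urine AUC (L/h) |
|---|---|---|---|
| 5 | 0.06 / 0.12 / 0.24 | 5 / 5 / 5 | 0.06 / 0.12 / 0.24 |
| 10 | 0.06 / 0.12 / 0.24 | 10 / 10 / 10 | 0.06 / 0.12 / 0.24 |
| 20 | 0.06 / 0.12 / 0.24 | 20 / 20 / 20 | 0.06 / 0.12 / 0.24 |

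The plasma version returns the true CLr at every flow. The urine version returns the flow and does not move when true CLr rises fourfold. With six 2-hour collections placed at interval midpoints and the SAP's linear-up/log-down rule, it still returns the flow, about 6 to 8% high.

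**3. Size with the protocol's own figures.** Inputs from Protocol Section 5.5: about 285 mg excreted in urine after a single 1500-mg dose (collection period not stated), and a minimum urine AUC over 12 h of 807 µg·h/mL, both from the same Phase I study.

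- Formula as written: 285,000 µg / 807 µg·h/mL = 353 mL/h = 0.353 L/h; 353/60 = 5.9 mL/min. Over 12 h this is 353 × 12 ≈ 4,240 mL. That is on the high side for urine output because a minimum AUC is set against an approximate typical amount. With 285 mg held fixed, any larger urine AUC makes the result smaller.
- With a plasma denominator the documents give no AUC, so the values below are assumed:

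| Assumed total plasma AUC(0-12) (µg·h/mL) | CLr = 285 mg / AUC (L/h) | Ratio to 0.353 L/h (= 807/AUC) |
|---|---|---|
| 5 | 57.0 | 161 |
| 10 | 28.5 | 81 |
| 20 | 14.25 | 40 |
| 40 | 7.1 | 20 |
| 50 | 5.7 | 16 |

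**4. Total or free.** If plasma is used but the free AUC (0.67 × total) is taken, CLr rises by 1/0.67 = 1.49-fold. The matrix alone therefore does not fix the number.

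**The case against.** The best defence is that this is a clash of symbols and not a wrong analysis. The protocol uses AUC(0-τ) only for plasma: its urine list in Section 9.5.1 contains no AUC. Under that notation Ae 12h/AUC(0-τ) is the standard formula. The SAP calls for standard non-compartmental practice, and an experienced pharmacokineticist would probably use plasma AUC. SAP Section 12.3.3 does not list urine AUC among the programmer's urine derivations, so it does not show which AUC would go into CLr. A result near 6 mL/min, in a study that excludes creatinine clearance below 30 mL/min, might well draw a query. CLr is one descriptive parameter in a single-arm study without hypothesis tests, it feeds no other analysis, and it can be recomputed from Listings 40 and 41.

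Much of this stands. The consequence is conditional on the table being followed literally. The primary plasma parameters, Ae and fe% are untouched. The 0.35 L/h is not a bound for every participant, since it pairs an approximate amount with a minimum AUC, and the fold differences rest on assumed plasma AUCs.

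It does not rescue the definition. Nowhere does the SAP say that the CLr denominator is plasma, and the only AUC(0-τ) in Table 3 is explicitly urine. The text above the table points to urine data alone. A reader who overrides the table with plasma must still choose between total and free.

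**Conclusion.** The concern holds. As written, SAP Table 3 defines renal clearance by a formula that yields concentration-weighted urine flow. The algebra needs no assumed values. The size does: about 0.35 L/h from the protocol's Phase I figures, against roughly 7 to 28 L/h if total plasma AUC(0-12) is 10 to 40 µg·h/mL, a gap of about 20- to 80-fold (16- to 161-fold over 5 to 50 µg·h/mL). The direction and the order of the discrepancy are the same throughout those ranges. The effect is confined to the secondary endpoint CLr on Days 1 and 4, and whether it would occur depends on whether the analyst follows the table or corrects it silently.

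**What to change.** - Rewrite the CLr row of SAP Table 3 as: CLr = Ae 12h (urine) / total plasma AUC(0-τ) from Table 2, for the same participant, day and dosing interval.
- If an unbound renal clearance is wanted, define and report it as a separate parameter using the free plasma AUC.
- Give the urine areas their own symbols, for example AUCu(0-τ) and AUCu(0-24). Carry them through Table 3, SAP Section 10, Tables 4.5 and 5.1, Figure 5.1 and Listings 41 and 42.
- Amend the text above Table 3 so that it allows CLr to draw on plasma data, and state the CLr inputs in SAP Section 12.3.3.

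The cost is SAP wording and a variable rename. No new samples, assays or participants are needed, because both inputs are already planned on Days 1 and 4.
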